Prospective, open-label study evaluating feasibility, safety and efficacy of Epclusa treatment in lung transplant recipients. Lung transplant recipients who are chronically infected with hepatitis C virus will be treated with Epclusa for 12 weeks and evaluated for evidence of hepatitis C virus in their blood at 12, 24 and 48 weeks after therapy initiation.

Individuals with chronic hepatitis C infection will be enrolled prior to transplant. Participation in this study will allow individuals with active chronic hepatitis C infection to be considered for candidacy for lung transplant, as chronic HCV infection has, until this study, been considered a contraindication for lung transplant at Duke.

Once the subject has undergone lung transplant, been discharged from the hospital and clinically stabilized (a process that can take weeks to months, depending on complications associated with this lung transplant), the subject will be referred for treatment screening. A regaining of functional status, increasing independence in activities of daily living, and a lack of significant or poorly controlled acute infections or need for hospitalization are markers of clinical stability which will be determined by the treating transplant pulmonologist.

If eligible, the subject will then be given study drug which will be taken for 12 weeks. Subject will be monitored throughout treatment course for adverse events. Upon completion of therapy, repeat testing will be performed to assess for clearance of the virus from the blood. Subjects will be followed for 48 weeks after initiation of study drug to monitor for recurrence and to evaluate change in degree of liver stiffness, as assessed by transient elastography.

Regimen (drug/dose/frequency)

Epclusa (sofosbuvir 400mg/velpatasvir 100mg) 1 tablet PO or VT daily x 12 weeks, taken with or without food.

Projected duration of treatment

12 weeks

Projected duration of enrollment

2 years

Study Details

- Treating pulmonologist will refer for treatment screening visit when clinically appropriate. Repeat HCV PCR and genotyping will be done prior to start of Epclusa treatment as part of the treatment screen.

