- Drug-drug interaction considerations: Many lung transplant recipients develop atrial fibrillation after lung transplant and may require treatment with amiodarone. Due to risk of bradycardia associated with concomitant use of epclusa and amiodarone, subjects must be off amiodarone for at least 60 days in order to be eligible for epclusa treatment.
- After 5 subjects complete 12 weeks of epclusa treatment, a preplanned analysis will be performed to assess safety and efficacy.
- HCV positive donors will have blood collected at time of procurement to be sent for genotyping and quantitative PCR.
- Because Epclusa is FDA-approved for all HCV genotypes, there is no anticipated safety risk associated with the organ donor having a different genotype than recipient.

Early discontinuation

If a subject decides to withdraw from the study prior to completion, the subject will be asked to return for a final visit for data collection.

Selection of Subjects

Inclusion criteria:

1. HCV RNA $\geq 10^3$ IU/ml at screening
2. Chronic HCV infection, defined as positive HCV antibody and/or HCV RNA more than 6 months prior to screening
3. HCV Genotype 1, 2, 3, 4, 5 or 6
4. Otherwise eligible for lung transplant at study site

Exclusion criteria:

1. Age < 18
2. Treatment with any of the following agents:
 - Amiodarone. Subjects previously treated with amiodarone must have stopped the amiodarone at least 60 days prior to day 1 SOF/VEL
 - Carbamazepine, phenytoin, phenobarbital, oxcarbazepine
 - Rifabutin, rifampin or rifapentine
 - HIV regimens containing tenofovir, tipranavir/ritonavir, or efavirenz
 - St John's wort
 - Modafinil

3. Have any serious or active medical or psychiatric illness which, in the opinion of the investigator, would interfere with subject treatment, assessment or compliance
4. Hepatitis B surface antigen positive (This is checked at the time of transplant evaluation.)
. (
5. History of hepatic encephalopathy or variceal hemorrhage
6. Abnormal hematological and biochemical parameters, including:
 - Hemoglobin <8g/dL
 - Platelets <= 50,000/mm³
 - ALT (alanine aminotransferase), AST (aspartate aminotransferase) or alkaline phosphatase >=10 times ULN
 - Total bilirubin >3mg/dL
 - Severe renal impairment, ie creatinine clearance (CrCl) <30mL/min
7. Pregnant women or women planning to become pregnant
8. Women who are breastfeeding
9. Active or recent history (<=1 year) of drug or alcohol abuse

Subject Recruitment and Compensation

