- If the subject is eligible to start Epclusa treatment a 6 week supply will be dispensed. A drug log will be provided to the subject for accountability purposes.
- Concomitant medications will be review
- Clinical data related to transplant and donor will be collected from subject’s medical chart.

Treatment Initiation

Subjects will be started on EPCLUSA treatment. Treatment consists of 1 pill taken by mouth once a day, either with or without food. Treatment will last 12 weeks. This visit can be combined with the treatment screening visit if subjects are eligible at that time.

Week 4

The following tests and procedures will be done at this visit as part of standard of care:

- Physical exam
- Vital Signs

Routine blood tests will be collected (CBC, CMP, Mg, and PT/INR). The following will be done at this visit for research purposes:

- Dispense 6 weeks supply of Epclusa.
- Drug accountability review
- Adverse Events (AE) assessment
- Concomitant medications review

Week 8

The following tests and procedures will be done at this visit as part of standard of care:

- Physical exam
- Vital Signs
- Routine blood tests will be collected (CBC, CMP, Mg, and PT/INR).

The following will be done at this visit for research purposes:

- AE assessment
- Concomitant medications review

Week 12

The following tests and procedures will be done at this visit as part of standard of care:

- Physical exam
- Vital Signs
- Routine blood tests will be collected (CBC, CMP, Mg, and PT/INR).

The following test and procedures will be done at this visit for research purposes:

- A blood sample will be collected for HCV status.
- Drug accountability review
- AE assessment
- Concomitant medications review

Week 24

The following tests and procedures will be done at this visit as part of standard of care:

- Physical exam
- Vital Signs
- Routine blood tests will be collected (CBC, CMP, Mg, and PT/INR).

The following test and procedures will be done at this visit for research purposes:

- A blood sample will be collected for HCV status.
- AE assessment
- Concomitant medications review

Week 48

The following tests and procedures will be done at this visit as part of standard of care:

- Physical exam
- Vital Signs
- Routine blood tests will be collected (CBC, CMP, Mg, and PT/INR).

The following test and procedures will be done at this visit for research purposes:

- A blood sample will be collected for HCV status.
- AE assessment
- Concomitant medications review

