- Transient Elastography

Schedule of Assessments

Study Week +/- 21 days	Lung transplant evaluation	Study Screening	Transplant	Treatment Screening Visit	Treatment initiation (can be combined with treatment screening)	Week 4	Week 8	Week 12	Week 24	Week 48
Study Informed consent		X								
Inclusion/Exclusio n		X								
Demographics		X								
Medical history				X						
Physical exam	X			X		X	X	X	X	X
Vital Signs Height/Weight	X			X		X	X	X	X	X
Confirm treatment eligibility				X						
Serum HCG				X						
Liver biopsy	X									
Transient elastography	X									X
HCV PCR	X			X				X	X	X
HCV genotype	X			X						
Routine labs (CBC, CMP, Mg, PT/INR)	X			X		X	X	X	X	X
Drug and alcohol Screen	X									
Hepatitis B Screen	X									
EKG	X			X						
Dispense Drug					X (6 week supply)	X (6 week supply)				
Review Con Meds				X		X	X	X	X	X
Review for AEs						X	X	X	X	X
Donor HCV PCR/genotype (if donor HCV NAT positive)			X (At time of procurement)							

*All follow-up visits may occur inpatient or outpatient.

*Boxes marked in red are part of standard of care for lung tx candidates/recipients.

Note: To ensure compliance with CMS guidelines, all studies involving patient care at Duke are required to have study protocol-specific EMR build for ordering, resulting and billing of protocol-related activities. This ensures SOC activities are billed to insurance and protocol-related activities are billed to the study. This is referred to as EPIC initiation. The EPIC build is specific to each protocol and will not be used for any future studies.

References

ⁱ <http://www.cdc.gov/nchs/fastats/copd.htm>

ⁱⁱ <https://www.unos.org/about/annual-report/>

ⁱⁱⁱ Doucette KE¹, Halloran K², Kapasi A², Lien D², Weinkauf JG². Outcomes of Lung Transplantation in Recipients with Hepatitis C Virus Infection. *Am J Transplant.* 2016 Mar 21 [Epub ahead of print].

^{iv} Englum BR¹, Ganapathi AM², Speicher PJ², Gulack BC², Snyder LD³, Duane Davis R², Hartwig MG². Impact of donor and recipient hepatitis C status in lung transplantation. *J Heart Lung Transplant.* 2016 Feb;35(2):228-35

^v J. Levitsky, K. Doucette. **AST Infectious Diseases Community of Practice.** Viral hepatitis in solid organ transplantation. *Am J Transplant*, 13 (Suppl 4) (2013) 147-68.

^{vi} Doucette K¹, Sumner S², Weinkauf J³. **Treatment of hepatitis C in a lung transplant recipient with sofosbuvir and daclatasvir.** *J Heart Lung Transplant.* 2016 Feb 8. pii: S1053-2498(16). [Epub ahead of print].

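### The +/- 21 day visit window is wider than the roughly 14 days of drug left at Week 4, so an in-window resupply visit could interrupt daily dosing by up to about 7 days

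*Combined protocol and SAP*

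**What the plan says.** The regimen in Design & Procedures is "1 tablet PO or VT daily x 12 weeks". Treatment Initiation repeats this: "Treatment consists of 1 pill taken by mouth once a day" and "Treatment will last 12 weeks".

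Drug is handed out twice. Under Treatment Screening Visit: "If the subject is eligible to start Epclusa treatment a 6 week supply will be dispensed". Under Week 4: "Dispense 6 weeks supply of Epclusa". The drug-dispensing row of the Schedule of Assessments table marks treatment initiation and Week 4 and no other column.

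The table header carries the only visit window in the document, "Study Week +/- 21 days". No tighter limit is given for Week 4. No interim resupply or shipment is described, and there is no rule for doses missed because drug ran out.

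Design & Procedures counts the virology visits from the start of treatment: "in their blood at 12, 24 and 48 weeks after therapy initiation". It does not say the same of Week 4 explicitly. The only day numbering for dosing is in the exclusion criteria, "at least 60 days prior to day 1 SOF/VEL", which makes the first dose day 1 but does not say which study day is Week 4.

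**The concern.** Supply and window were set separately and do not fit together. The supply tolerates about two weeks of lateness at Week 4; the window allows three. A site could keep every visit in window, dispense exactly as written, and still have a subject without tablets partway through a once-daily course.

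What is at stake is an uninterrupted 12-week course, on which the primary SVR12 endpoint rests. The protocol does not say what happens to tablets left over after a gap. One subject might finish them late and another stop at 12 weeks with some untaken. In a study of 10 subjects, such an irregularity would need explaining case by case. The secondary endpoint on temporary interruption covers only interruptions required by adverse events, so a supply gap would not be counted there.

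**Working it through.** **Inputs**
- First supply: 6 weeks x 7 = 42 tablets (Treatment Screening Visit; schedule table).
- Second supply: 42 tablets, at Week 4 (Week 4; schedule table).
- Dosing: 1 tablet a day for 12 weeks (Regimen; Treatment Initiation).
- Window: 21 days either side (schedule table header).
- Assumption: Week 4 is counted from the first dose, as Weeks 12, 24 and 48 are.

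**The plan's own total.** 2 x 42 = 84 tablets, and 12 x 7 = 84 doses. The total is exactly right, so the issue is only when the second half arrives.

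**Buffer against window.** Buffer at the nominal visit = 42 - 28 = 14 days. Latest in-window visit = 28 + 21 = 49 days after the first dose. Excess = 49 - 42 = 7 days.

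**Day counting.** Number the first dose as day 1, so the first supply covers days 1 to 42. Let L be the days late, and R the first day on which the second supply is used. The gap is max(0, R - 43). Two things are unstated: whether Week 4 means 28 days elapsed (day 29) or day 28, and whether the new supply is used on the visit day or from the next day. The four combinations are:
- A: day 29, same-day restart. R = 29 + L; gap = max(0, L - 14)
- B: day 29, next-day restart. R = 30 + L; gap = max(0, L - 13)
- C: day 28, same-day restart. R = 28 + L; gap = max(0, L - 15)
- D: day 28, next-day restart. R = 29 + L; gap = max(0, L - 14)

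Gap in days:

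| Days late | A | B | C | D |
|---|---|---|---|---|
| 0 | 0 | 0 | 0 | 0 |
| 13 | 0 | 0 | 0 | 0 |
| 14 | 0 | 1 | 0 | 0 |
| 15 | 1 | 2 | 0 | 1 |
| 16 | 2 | 3 | 1 | 2 |
| 18 | 4 | 5 | 3 | 4 |
| 21 | 7 | 8 | 6 | 7 |

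The window holds 43 calendar days (21 + 1 + 21). A gap arises on 7, 8, 6 and 7 of them under A to D. These are counts of permitted days and say nothing about how often a visit would be that late.

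**What a gap does to the course.** At 21 days late, if every tablet is eventually taken, the last dose falls on day 84 + gap: day 91, 92, 90 or 91. If treatment stops at day 84, tablets taken = 84 - gap: 77, 76, 78 or 77. The documents do not say which applies.

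**Check of the remedies**
- Late limit of +13 days: gap 0 under all four counts.
- Late limit of +14 days: gap 0 under A, C and D, but 1 day under B.
- Full window kept, first supply of 49: the latest R is 50, 51, 49 or 50, against tablets lasting to day 49. Gap 0, 1, 0, 0.
- Full window kept, first supply of 50: gap 0 under all four, with 84 - 50 = 34 tablets at Week 4.

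**The case against.** A window is a permission, and it does not cancel the dosing rule. A site has to satisfy both, and on 35 to 37 of the 43 in-window days it can do so with no change to the protocol. The plan also already covers two weeks of lateness by giving six weeks of drug before a four-week visit. A gap needs a visit later than that and also a site that does nothing about an empty bottle. Study visits are to be coordinated with routine care where possible and may take place inpatient or outpatient. Subjects keep a drug log, and accountability is reviewed at Weeks 4 and 12.

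Most of this stands, and it is why the point is minor. It does not remove the mismatch: the log and reviews record a gap but do not prevent one, and off-schedule resupply is left to initiative.

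A reader might infer three stronger things that the documents do not support.
- That subjects will lose drug. All 84 tablets are still dispensed; a gap is possible, not certain, and off-schedule resupply is not forbidden.
- That SVR12 would suffer. Nothing in the documents links a gap of this length to response, so no effect can be stated.
- That the interruption is exactly 1 to 7 days for visits 15 to 21 days late. That holds under two of the four day counts; the others give 0 to 6 and 2 to 8.

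**Conclusion.** The concern holds as a small conflict between the written dispensing schedule and the written visit window. A Week 4 visit more than about two weeks late is in window and could leave a subject without drug for up to about 7 days, with a range of 6 to 8 at the extreme of the window.

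This rests on three assumptions: the header window applies to the Week 4 column, Week 4 is counted from the first dose, and no one resupplies off schedule. The first is the plain reading, since no other window is given. The second is a reasonable inference from how the later visits are counted. The third is not settled by the protocol either way. Confidence in the arithmetic is high. How often it would matter cannot be estimated from the documents and is probably low. Severity: minor.

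**What to change.** Keep +/- 21 days for the other visits. At Week 4, add that resupply must take place before the first 42 tablets run out, with a late limit of no more than +13 days. A limit of +14 days is enough only if a tablet from the new supply is taken on the visit day, and the text should then say so.

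The cost is one line in the schedule table or the Week 4 text. The Week 4 window falls from 43 days to 35 (21 + 1 + 13), so scheduling is slightly less flexible at that one visit. Visits, subjects and tablets are unchanged.

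If the full window is wanted at Week 4, the alternative is a larger first supply within the same 84 tablets, for example 50 and then 34. This depends on pack size, which the documents do not give, and it makes the two dispensings uneven.

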Protocol Title

Lung Transplantation in Chronic Hepatitis C Infection with Post Transplant EPCLUSA Treatment: A Pilot Feasibility and Efficacy Study

Purpose of the Study

Primary objectives

- Assess feasibility, safety and efficacy of Epclusa treatment after lung transplant in those with chronic Hepatitis C Virus infection.
- Establish Sustained Virologic Response (SVR)12 rates in HCV-infected lung transplant recipients treated with EPCLUSA. SVR 12 is the absence of detectable hepatitis C virus in the blood after 12 weeks of antiviral therapy. This is the standard outcome in studies evaluating therapies to treat hepatitis C virus.

Secondary Objective

- Evaluate impact of considering donors who are hepatitis C nucleic acid amplification test (NAT) positive in recipients with pre-existing hepatitis C viremia on wait times and post transplant survival.
 - Are wait times shortened by considering HCV NAT positive donors?
 - Do HCV NAT positive donors otherwise meet criteria for lung donation?

Primary endpoints

- Sustained Virologic Response 12 weeks (SVR 12) in those treated with EPCLUSA
- Adverse events resulting in discontinuation of EPCLUSA
- Eligibility for EPCLUSA treatment within 12 months of lung transplant.
 - If subjects do not have adequate renal function or require medications with significant drug interactions with epclusa, they will not be eligible for treatment. Eligibility is an outcome because it is not known if these factors will limit utility of epclusa in this setting due to common complications associated with lung transplantation.

Secondary endpoints

- Serum HCV RNA levels at 12-, 24-, and 48-weeks after initiation of EPCLUSA
- Adverse events requiring temporary interruption in Epclusa therapy
- 90-day and 1-year post transplant patient survival
- 90-day and 1-year post transplant patient survival in recipients of HCV NAT positive donor organ

Exploratory outcomes

- Change in transient elastography score at 48-weeks post Epclusa treatment

- Acute rejection rates
- Primary graft dysfunction scores
- Infections requiring treatment
- Wait times associated with donor HCV status

Background & Significance

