Epclusa is a fixed-dose combination product containing sofosbuvir, an HCV NS5B polymerase inhibitor, and velpatasvir, an HCV NS5A inhibitor. It was approved by the FDA in June 2016 for the treatment of chronic HCV genotypes 1, 2, 3, 4, 5 and 6. The first antiviral approved to treat all major forms of HCV, it can be used in patients with compensated and uncompensated cirrhosis, as well as those without cirrhosis. Response rates, defined as a RCV RNA pcr less than the lower limit of quantification (<LLOQ) 12 weeks after completion of therapy (SVR12), in those without decompensated cirrhosis who were treated for 12 weeks range from 94-99%. It is recommended as first line therapy by the American Association for the Study of Liver Diseases (AASLD) and the Infectious Diseases Society of America (ISDA) for treatment of chronic HCV infection with genotypes 1, 2, 3, 4, 5 and 6.

The goal of this study is to assess whether a strategy of performing lung transplant in individuals with end stage lung disease and chronic HCV infection, and then treating them post-transplant with Epclusa is feasible, safe and effective at curing HCV.

The reason to wait until after lung transplant to treat the hepatitis C virus is two-fold. First, it opens up the donor pool to include those with chronic hepatitis C. This can potentially shorten wait times and increase the number of lungs used for transplantation, which could increase access to a life-saving transplant and for those suffering with end stage lung disease and decrease deaths on the waiting list. The second reason to adopt this strategy is that it allows those with rapidly progressive lung disease to be transplanted prior to completing 12 weeks of antiviral

therapy, during which time their lung disease might progress to the point where they are too sick to survive a lung transplant.

As a first step, this study includes only lung transplant candidates with chronic HCV infection. For these candidates with chronic HCV infection, consideration would be given to organ offers from both HCV NAT positive and HCV NAT negative donors. Donors would be accepted based on quality and suitability, independent of HCV status. *There would be no intentional utilization of an HCV positive donor into an HCV negative recipient.*

Design & Procedures

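### SVR12 is worded two ways, differing in timing and threshold, and no visit is named for it; the visit window lets the nominally matching Week 24 PCR fall about 9 weeks off drug

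*Combined protocol and SAP*

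**What the plan says.** All references are to the combined protocol and SAP.

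- **Primary objectives:** "SVR 12 is the absence of detectable hepatitis C virus in the blood after 12 weeks of antiviral therapy". The Primary endpoints list then names SVR12 without a visit, time anchor or threshold.
- **Background & Significance**, describing published response rates for the drug: HCV RNA below LLOQ "12 weeks after completion of therapy (SVR12".
- **Secondary endpoints:** "Serum HCV RNA levels at 12-, 24-, and 48-weeks after initiation of EPCLUSA". Design & Procedures uses the same clock: subjects are "evaluated for evidence of hepatitis C virus in their blood at 12, 24 and 48 weeks after therapy initiation".
- **Schedule of Assessments table:** HCV PCR is marked at Weeks 12, 24 and 48. None is labelled SVR12. The header carries the only window: "Study Week +/- 21 days".
- **Endpoints that imply a moving last dose:** "Adverse events resulting in discontinuation of EPCLUSA" (primary) and "Adverse events requiring temporary interruption in Epclusa therapy" (secondary).
- **Data Analysis & Statistical Considerations:** descriptive and non-parametric statistics, with no SVR12 visit, analysis window or rule for an early sample.

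**The concern.** The two wordings can classify the same subject differently.

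- **Timing.** The objectives' wording states no post-treatment interval, so it can be read as response at the end of treatment. The Background wording requires 12 weeks off drug.
- **Threshold.** RNA that is detectable but below LLOQ fails the objectives' wording and passes the Background wording.

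The window matters under either reading. An end-of-treatment response, or a response about 9 weeks off drug, could be reported as SVR12. A relapse first detectable between an early Week 24 draw and 12 weeks off drug would then count as success. A late draw can err the other way, because a relapse first detectable after 12 weeks but before the draw would count as failure.

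Establishing SVR12 rates is a stated primary objective, and the study enrols 10 subjects, so each classification carries weight. The preplanned safety and efficacy analysis (Study Details) comes after 5 subjects complete 12 weeks of treatment. At that point some may have only a Week 12 PCR, and the plan does not say which measure of efficacy applies.

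**Working it through.** The plan gives no figure of its own to reproduce.

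**Inputs.** Treatment lasts 12 weeks = 84 days, and PCRs fall at Weeks 12, 24 and 48 from initiation (Design & Procedures). The window is ±21 days (Schedule of Assessments). The target is 12 weeks = 84 days off drug (Background & Significance).

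**Assumption.** The first dose is Day 1; the documents give no day numbering. The last dose of an uninterrupted course is then L = Day 84, and Week w falls on Day 7w + 1. Counting from Day 0 would shift the results by about one day.

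**Nominal check.** 24 − 12 = 12 weeks, so Week 24 is the visit that matches the Background interval.

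**Windows, uninterrupted course** (days off drug = visit day − 84):

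| Visit | Nominal day | Window | Days from last dose | Weeks |
|---|---|---|---|---|
| Week 12 | 85 | 64–106 | −20 to +22 | about −3 to +3 |
| Week 24 | 169 | 148–190 | 64 to 106 | about 9 to 15 |
| Week 48 | 337 | 316–358 | 232 to 274 | about 33 to 39 |

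**Early part of the Week 24 window.** A draw reaches 84 days off drug from Day 84 + 84 = 168. Days 148–167 are short: 20 days. Days 168–190 qualify: 23 days. 20 + 23 = 43.

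**If the last dose moves.** Every in-window Week 24 draw qualifies if 148 − L ≥ 84, so L ≤ 64. None qualifies if 190 − L < 84, so L > 106. Between these limits the number of qualifying days is 107 − L: 23 at L = 84, 16 at L = 91, 9 at L = 98 and 2 at L = 105. The documents do not say whether interrupted doses are made up, so the later values of L are illustrations.

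**Size of the effect on the rate.** The documents give no visit-timing data and no rate of relapse first detectable at 9 to 12 weeks, so the bias cannot be computed. For scale only, take the 94–99% response in Background & Significance, which is not from lung recipients, and suppose all 10 are treated:

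- Expected failures of any kind: 10 × 0.01 = 0.1 to 10 × 0.06 = 0.6.
- Chance of at least one: 1 − 0.99^10 = 9.6% to 1 − 0.94^10 = 46.1%.
- One misclassified subject moves the rate by 1/10 = 10 points: 10/10 (exact 95% CI 69.2–100%) instead of 9/10 (55.5–99.7%).

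Only some failures would be relapses first detectable in that interval.

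**The case against.** **Week 24 can be inferred.** The objectives call SVR12 the standard outcome in hepatitis C studies, the Background gives an explicit interval, and the Week 24 PCR nominally falls 12 weeks after a 12-week course. This stands as the more natural reading. A reader might go further and infer that the trial intends the Week 12 PCR as its primary endpoint. The documents do not support that: they leave it possible by wording but never say it. Nor does the Background sentence settle the matter, since it describes published results and not this trial's endpoint, and the inference does not resolve the threshold.

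**Relapse will be seen anyway.** Design & Procedures states "Subjects will be followed for 48 weeks after initiation of study drug to monitor for recurrence", and a PCR is scheduled at Week 48. This stands for subjects sampled then, so it would be wrong to infer that relapses go unseen in general. What remains is that no rule links Week 48 to SVR12, a subject who dies earlier has no later sample, and the final visit for those who withdraw (Early discontinuation) lists no PCR.

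**The effect is small in an unpowered pilot.** The analysis is descriptive with no success threshold, and fewer than 10 may be treated, because treatment eligibility is itself an endpoint. This stands. A reader might infer from the 20 of 43 days that about half the results would be mistimed, or that the SVR12 rate is materially inflated. The count describes permitted days, not when visits occur, and gives no bias.

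**The window need not be narrowed.** Week 24 is also a standard-of-care visit, and Costs to the Subject promises every attempt to fit study visits to routine care. This stands: classifying samples by days since last dose deals with the problem without a compulsory one-sided window.

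**Conclusion.** The point holds. A primary endpoint has two wordings that conflict in timing and threshold, and no visit is attached to either; the passages must be reconciled. The definition is the main defect and the window is secondary to it.

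For an uninterrupted course, an in-window Week 24 PCR can be about 3 weeks short of 12 weeks off drug, and a Week 12 PCR can precede the end of therapy by about 3 weeks. An interruption that delays the last dose enlarges the Week 24 shortfall. The exact day counts rest on the assumed Day 1 convention; the figure of about 3 weeks does not depend on it.

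The effect on the reported rate is probably small and cannot be computed. The change is still worth making, because the ambiguity is in a primary endpoint and costs little to remove.

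**What to change.** 1. **One definition.** Reconcile the Primary objectives with Background & Significance, with one stated threshold: for example, HCV RNA below LLOQ at least 84 days after the actual last dose. Name Week 24 as its visit. Report the Week 12 PCR separately as end-of-treatment response, labelled on- or post-treatment.
2. **Classify by time off drug.** Record the actual last-dose date from the drug log and confirm it at Week 24, since accountability review is last listed at Week 12 and may precede the last dose. Classify each PCR by days since last dose, and use the first sample at least 84 days off drug, subject to rule 3.
3. **Rule for a Week 24 sample under 84 days off drug:**
   - Quantifiable RNA off treatment is not SVR12, whatever Week 48 shows.
   - If it is below LLOQ and Week 48 is also below LLOQ, this supports SVR12.
   - If it is below LLOQ and Week 48 is quantifiable, count as not SVR12 and report as relapse of undetermined timing.
   - If it is below LLOQ and there is no later sample, count as not SVR12, with a sensitivity analysis the other way.
4. **Scheduling preference.** Where possible, aim the Week 24 draw at 84 or more days off drug within the present window (Day 168–190 for an uninterrupted course). This is preferred, not required.

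**Cost.** One definition, one analysis rule and a scheduling note, using PCRs already planned and drug logs already kept. The preference leaves 23 of 43 days and may conflict with coordinating visits with routine care. Subjects drawn early rely on Week 48, which cannot date a relapse. Subjects who stop early are assessed well beyond 12 weeks off drug: with an illustrative last dose on Day 28, a Week 24 draw is 148 − 28 = 120 to 190 − 28 = 162 days off drug, about 17 to 23 weeks. The off-drug interval should therefore be reported for each subject.
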